3.3 Study Subjects

3.3.1 Subject Disposition and Completion Status

A summary of subject eligibility and randomization (including a summary of subjects randomised but not treated with double-blind investigational product) as well as treatment administered will be provided. In addition, disposition of subjects throughout the study with respect to completion of treatment and end of study will be provided.

3.3.2 Demographics and Baseline Characteristics

Demographic information related to sex, age, race, weight, height, and body mass index (BMI) will be presented by treatment group and for all subjects combined. A summary of baseline disease characteristics may include duration of diabetes, specified diabetes complications, and smoking and alcohol history.

3.3.3 Study Drug Exposure

The number of doses and total dose received will be summarized for each investigational product (MEDI0382 or placebo) by descriptive statistics and frequencies.

3.3.4 Concomitant Medications

Concomitant medications will be coded using the current WHO Drug Dictionary enhanced (WHO-DD). The number and percentage of subjects who took concomitant medications for the highest anatomical therapeutic chemical (ATC) class and preferred term will be summarized by study part and treatment for the As-treated population. The summary of concomitant medications will include all concomitant medications taken on or after the date of first dose of investigational product or any concomitant medication started prior to first dose of investigational product that continued beyond the date of first dose of investigational

product. Concomitant medications will be summarized separately for the double-blinded treatment period and for the single-blinded treatment period.

3.4 Efficacy Analyses

3.4.1 Primary Efficacy Endpoint(s) and Analyses

3.4.1.1 Primary Efficacy Endpoint(s)

Percentage change in body weight in kg from Day 17 to 59

3.4.1.2 Handling of Dropouts and Missing Data

If a subject has a missing Day 17 (baseline) weight value, the last weight value prior to Day 17 will be used as the baseline in the analysis. If a subject has a missing weight value on Day 59, the subject will be included in the analysis using the last value after the start of the double-blind period, ie, last observation carried forward (LOCF).

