4.1.6 Discontinuation of Investigational Product

An individual subject will not receive any further investigational product if any of the following occur in the subject in question:

- 1 Withdrawal of consent from further treatment with investigational product
- 2 Lost to follow-up
- 3 An AE that, in the opinion of the investigator or the sponsor, contraindicates further dosing: specific examples include:
 - Dose-limiting symptoms with respect to GI tolerability and in particular if a subject requires intravenous fluids for more than 48 hours to treat volume depletion

secondary to nausea and vomiting, even after measures are taken to reduce the risk of vomiting, after discussion with the medical monitor

- Any subject where Hy's law criteria on liver function tests is met: AST or ALT $\geq 3 \times$ ULN **together with** total bilirubin $\geq 2 \times$ ULN
 - Any subject who develops a life-threatening arrhythmia including sustained ventricular tachycardia, ventricular fibrillation or new ECG changes of second or third-degree heart block
 - Subjects with persistent fasting glucose level of > 260 mg/dL (14.4 mmol/L) despite a maximum tolerated dose of rescue therapy to enable optimisation of the subject's glycaemic control
- 4 Subject noncompliance that, in the opinion of the investigator or sponsor, warrants withdrawal (eg, refusal to adhere to scheduled visits)
 - 5 Pregnancy in a female subject

Subjects who are permanently discontinued from receiving investigational product will be followed for protocol-specified assessments including follow-up of any AEs unless consent is withdrawn from further study participation (Section 4.1.5), the subject is lost to follow-up, the subject starts alternative treatment, or the subject is enrolled in another clinical study.

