4.2.4 Early Discontinuation Visit or Unscheduled Study Visit

The following study procedures may be conducted for subjects who prematurely discontinue from the study or for subjects who require an unscheduled study visit. The types of procedures required will be at the discretion of the investigator.

- Targeted physical examination
- ECG

- Vital signs
- Body weight
- [REDACTED]
- Blood tests including chemistry and haematology panel
- [REDACTED]
- Assessment of AEs/serious adverse events (SAEs)
- Concomitant medications
- Urine pregnancy test (if applicable)

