4.8.4 Efficacy

4.8.4.1 Primary Efficacy Analysis

The efficacy analysis will be based on the mITT population. The primary efficacy endpoint of percentage change in body weight from Day 17 to 59 will be compared between MEDI0382 and placebo groups using an analysis of covariance (ANCOVA) model adjusting for treatment group and measurement at baseline. Last observation carried forward will be used for missing data imputation for post-baseline values when applicable.

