2.4 Sample Size

Sixteen subjects in the MEDI0382 group and 8 subjects in the placebo group will provide > 90% power to detect a 2.5% weight change from baseline difference between [REDACTED] and placebo at Day 59, assuming a standard deviation of 2.0%, a 2-sided 0.1 alpha.

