3 STATISTICAL METHODS

3.1 General Considerations

Data will be presented in data listings sorted by treatment, subject number and date collected, where appropriate. Tabular summaries will be presented for each treatment. Categorical data will be summarized by treatment with the number and percentage of subjects within each category. Continuous variables will be summarized by treatment with descriptive statistics including mean, standard deviation, median, minimum, and maximum. For some variables, the geometric mean and 95% CI will be presented. Baseline values will be defined as the last valid assessment prior to the first administration of investigational product unless otherwise specified.

All available data will be included in the analyses and missing data will not be imputed, except in a last observation carried forward (LOCF) analysis and as specified in the calculation of the AUC values. When last observation carried forward (LOCF) is used to impute for missing post-baseline data, only post-baseline data will be carried forward (e.g., baseline data will not be carried forward).

All statistical tests will be 2-sided at an $\alpha = 0.10$ significance level unless stated otherwise. There will be no adjustment for multiplicity.

Data analyses will be performed using SAS[®] version 9.4 or higher (SAS Institute Inc., Cary, NC). The analytical results generated from SAS programs will follow MedImmune SAS programming standards and will be validated according to MedImmune SAS validation procedures.

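### The primary LOCF rule does not say which weights may be carried forward; if only clinic weights count, a 15-day change can stand as the 42-day result and subjects without a post-baseline weight have no place

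*SAP*

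**What the plan says.** The primary endpoint is percentage change in body weight from Day 17 to Day 59, compared by ANCOVA with treatment and baseline weight in the mITT population (SAP 3.4.1.1 and 3.4.1.3). That population needs one double-blind dose and no post-baseline weight (SAP Table 1).

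- **Missing Day 59 weight.** SAP 3.4.1.2: "the subject will be included in the analysis using the last value after the start of the double-blind period, ie, last observation carried forward". Protocol 4.8.4.1 agrees: "Last observation carried forward will be used for missing data imputation for post-baseline values when applicable".
- **Limit on carrying forward.** SAP 3.1: "only post-baseline data will be carried forward (e.g., baseline data will not be carried forward".
- **Weights available.** Protocol Table 6 schedules clinic weights on Days -1, 17 (predose), 32 and 59. Visits on Days 21 and 25 have none. Subjects also weigh themselves at home every 72 hours (Table 6 and Protocol 4.3.2.8), and a weight is taken at Visit 10, 28 days (± 3) after the last dose (Table 7).
- **Early discontinuation.** Protocol 4.2.4 lists body weight among procedures that may be done, but "The types of procedures required will be at the discretion of the investigator".
- **After stopping drug.** Protocol 4.1.6 continues the scheduled assessments unless consent is withdrawn, "the subject is lost to follow-up, the subject starts alternative treatment, or the subject is enrolled in another clinical study".

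Neither document gives a drop-out rate, a rule for an mITT subject with no post-baseline weight, or a sensitivity analysis for the primary endpoint. The Per-protocol analysis is planned for selected secondary endpoints only (SAP 3.4.2.3).

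**The concern.** The rule turns on one undefined term, the last value, and each reading has a weakness.

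1. **Scheduled clinic weights only.** A subject who leaves between Day 32 and Day 59 contributes a 15-day change, treated as an observed 42-day change. A subject who leaves before Day 32 has nothing to carry, because baseline may not be used. SAP 3.4.1.2 says such a subject will be included; SAP 3.1 leaves no value with which to do it.
2. **Home weights allowed.** The carried value lies closer to the exit date, but a home-scale reading is then set against a calibrated clinic baseline.
3. **Any later weight.** Taken literally, the wording could admit Visit 10, which is measured off treatment.

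The plan expects some losses. Gastrointestinal intolerance is a named reason for stopping drug (Protocol 4.1.6), nausea and vomiting are summarised for each day of titration, Days 17 to 28 (SAP 3.7.1), and up to five subjects may be replaced (Protocol 4.1.7). With 24 subjects, a few imputed or excluded values can move the estimate. A choice among the readings made after the data are seen would be hard to defend.

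**Working it through.** **Inputs from the plan.** SAP 2.4: "Sixteen subjects in the MEDI0382 group and 8 subjects in the placebo group", "> 90% power to detect a 2.5% weight change from baseline difference", "assuming a standard deviation of 2.0%, a 2-sided 0.1 alpha". Protocol Table 6: baseline Day 17, intermediate clinic weight Day 32, endpoint Day 59.

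**Assumptions, not in the documents.** The arms diverge linearly from Day 17 to Day 59; losses occur only in the MEDI0382 arm; the SD stays at 2.0; nobody is replaced; 2 to 4 of 16 subjects are affected.

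**Step 1: the plan's own figure.** Standard error = 2.0 × √(1/16 + 1/8) = 0.866. Noncentrality = 2.5/0.866 = 2.887. Two-sided power at alpha 0.10 is 89.3% by the normal approximation and 87.5% by the noncentral t with 22 df. That is close to the stated figure, though not strictly above 90% without some gain from the covariate (a baseline correlation of 0.3 gives 90.0%). The shortfall is a separate matter; 87.5% serves here only as the reference.

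**Step 2: what a Day 32 value holds.** (32 − 17)/(59 − 17) = 15/42 = 35.7% of the effect, or 0.357 × 2.5 = 0.89 points.

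**Step 3: k of 16 active subjects carried from Day 32.** Expected difference = 2.5 − (k/16) × 2.5 × (27/42).

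**Step 4: k active subjects excluded for want of a value.** Difference held at 2.5, group sizes 16 − k and 8.

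| k | Difference if carried | Power if carried | Power if excluded |
|---|---|---|---|
| 0 | 2.50 | 87.5% | 87.5% |
| 2 | 2.30 | 82.3% | 86.0% |
| 3 | 2.20 | 79.2% | 85.0% |
| 4 | 2.10 | 75.9% | 83.9% |

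The last column counts only the smaller sample. It takes no account of selection if those who leave early differ from those who stay.

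**Step 5: sensitivity to the assumptions, k = 4.**
- Value carried from Day 45 instead (28/42 of the effect): difference 2.5 − 0.25 × 2.5 × 14/42 = 2.29, power 82%.
- Value carried from Day 52 (35/42): difference 2.5 − 0.25 × 2.5 × 7/42 = 2.40, power 85%.
- Four replacements added to the active arm, all 20 kept in mITT, Day 32 carried for four: difference 2.5 − (4/20) × 2.5 × 27/42 = 2.18, power 81%.

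**The case against.** A reader might infer that early drop-outs necessarily fall out of the analysis and that later ones necessarily carry Day 32. The documents do not support that. Stopping drug is not leaving the study, and scheduled assessments continue by default, so Day 59 may still be measured. Home weights, about five between Day 17 and Day 32, are not excluded by SAP 3.4.1.2, and a discontinuation visit may add a later clinic weight. Step 5 shows how much smaller the loss is if the carried value lies near the exit date or withdrawn subjects are replaced.

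A reader might also infer that LOCF always works against the drug. Carrying Day 32 dilutes the effect if weight loss continues, but excluding early active-arm leavers could favour the drug. The net direction is not fixed.

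The Visit 10 reading is narrow too. For anyone dosed beyond about Day 31 to 34 that visit falls after Day 59, so using it would carry a value backward. It fits a forward carry only for earlier stoppers.

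Finally, this is an exploratory 24-subject study at alpha 0.10, and LOCF is prespecified consistently in both documents. That limits the severity. It does not supply a definition of eligible weights, a rule for subjects without one, or a sensitivity analysis.

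**Conclusion.** The point holds in a conditional form. The SAP leaves the carried value undefined, gives no workable rule for an mITT subject without a post-baseline weight, and offers no check on the primary result. If only scheduled clinic weights count, a 15-day change can be analysed as a known 42-day change. Under the stated assumptions, 2 to 4 such subjects cost about 5 to 12 points of power (87.5% to 82.3% or 75.9%) and 0.2 to 0.4 points of the expected difference. Exclusion costs about 1.6 to 3.7 points of power, plus possible selection bias. These figures are illustrations: no drop-out rate is given, and continued follow-up, home weights or discontinuation weights may make the problem small. The change should be made because it is cheap and the ambiguity bears on the primary endpoint.

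**What to change.** - **Primary analysis.** Fit a likelihood-based repeated-measures model to percentage change from Day 17 at Days 32 and 59, with treatment-by-visit, baseline weight (or baseline-by-visit), unstructured covariance and Kenward-Roger degrees of freedom, and report the Day 59 contrast. Log weight at Days 17, 32 and 59, back-transformed, is an alternative. A model on raw weights would give a contrast in kg, which is not the primary endpoint. State the missing-at-random assumption.
- **Sensitivity analysis.** Keep the LOCF ANCOVA, restricted to clinic weights (scheduled or discontinuation visit) up to Day 59, without home or Visit 10 weights. Report by arm how many mITT subjects have no post-baseline weight.
- **Data collection.** Make body weight a required item at the early discontinuation visit. Obtain the Day 59 weight from every consenting subject, whatever their investigational product or alternative-treatment status, and state whether the estimand uses off-treatment weights.

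The cost is SAP wording, one extra model, a protocol change to Sections 4.1.6 and 4.2.4, and a weighing that the protocol already lists. The analysis then relies on missing at random, which cannot be tested. Baseline-only subjects add nothing to the percentage-change model and little to the log-weight model, so the required weighings matter more than the choice of model.

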3.4.1.3 Primary Efficacy Analysis

The analysis of the primary efficacy endpoint will be performed using the mITT population. The primary efficacy endpoint of percentage change in body weight from Day 17 to 59 will be compared between MEDI0382 and placebo groups using an analysis of covariance (ANCOVA) model adjusting for treatment group and baseline weight. LOCF will be used for missing data imputation if the Day 59 evaluation is missing.

3.4.2 Secondary Efficacy Endpoint(s) and Analyses

3.4.2.1 Secondary Efficacy Endpoint(s)

- Percentage and absolute change in total energy intake in kJ from the ad libitum lunch from Day 16 to 32 and Day 16 to 59
- Percentage and absolute change in total energy intake in kJ during the ad libitum lunch from Day -1 to 16
- Percentage and absolute change in TEE, AEE, and REE as measured by whole room indirect calorimetry in kJ per kg of fat body mass from Day 15 to 58
- Percentage and absolute change in REE as measured by hood indirect calorimetry in kJ per kg of fat body mass in kJ from Day 16 to 32
- Percentage and absolute change in total energy expenditure as measured by doubly labelled water in kJ per kg of fat body mass from baseline (Day 17) to the end of treatment (Day 58 or 59)
- Absolute change in body weight in kg from Day 17 to 59
- Change in absolute and percentage change in total body fat mass as measured by DXA in kg from Day -1 to 59
- Change in absolute and percentage change in total body fat mass: lean mass ratio as measured by DXA from Day -1 to 59
- Change in fasting glucose during a MMTT from Day -1 to 59

- Percentage change in glucose AUC_{4h} during a MMTT from Day -1 to 59

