**An Exploratory Phase 2a, Randomised, Double-blind,
Placebo-controlled Study to Evaluate the Effect of MEDI0382 on
Energy Balance in Overweight and Obese Subjects with Type 2
Diabetes Mellitus**

Sponsor Protocol Number: D5670C00021

Application Number: EudraCT number 2018-001220-19

Investigational Product: MEDI0382

Sponsor: MedImmune Limited, a wholly owned subsidiary of
AstraZeneca, [name]

Medical Monitor: [name], PhD
Medical Monitor, MedImmune
[contact]; [contact]

Contract Research Organization: Covance, Inc.

Protocol History, Date: Original Protocol, 19Apr2018
Amendment 1, 23May2018
Amendment 2, 17Jul2018
Amendment 3, 20Aug2018
Amendment 4, 31Aug2018
Amendment 5, 20Mar2019

This document contains trade secrets and commercial information that is privileged or confidential and may not be disclosed without prior authorization from MedImmune.

PROTOCOL SYNOPSIS

TITLE		
An Exploratory Phase 2a, Randomised, Double-blind, Placebo-controlled Study to Evaluate the Effect of MEDI0382 on Energy Balance in Overweight and Obese Subjects		
HYPOTHESES		

Primary Hypothesis: Administration of MEDI0382 once daily titrated up to a dose level of [REDACTED] will result in negative energy balance as evidenced by weight loss versus placebo after 42 days of treatment in overweight and obese subjects with type 2 diabetes mellitus (T2DM).
 
Secondary Hypotheses: Administration of MEDI0382 once daily titrated up to a dose level of [REDACTED] in overweight and obese subjects with T2DM will:
 
 • result in a reduction in energy intake versus placebo after 42 days of treatment • result in an increase in energy expenditure (EE) versus placebo after 41 days of treatment • result in a change in body composition (reduced body fat) versus placebo after 42 days of treatment • result in a reduction in fasting and post-prandial glucose versus placebo after 42 days of treatment • be well-tolerated in overweight and obese subjects 		
OBJECTIVES AND ENDPOINTS		
Type	Primary Objective	Primary Endpoint
Efficacy	To assess the effect of MEDI0382 titrated up to a dose level of [REDACTED] on body weight versus placebo	Percentage change in body weight in kg from Day 17 to 59
Type	Secondary Objectives	Secondary Endpoints

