2.2 Secondary Objectives and Endpoints

Table 2 Secondary Objectives and Endpoints

Type	Objective	Endpoint
Efficacy	To assess the effect of [REDACTED] versus placebo on energy intake during ad libitum lunchtime meals	Percentage and absolute change in total energy intake in kJ from the ad libitum lunch from: 
 Day 16 to 32 Day 16 to 59
Efficacy	To assess the effect of [REDACTED] versus placebo on TEE, AEE, and REE	Percentage and absolute change in TEE, AEE, and REE as measured by whole room indirect calorimetry in kJ per kg of fat body mass from Day 15 to 58
Efficacy	To assess the effect of a 16-day period of [REDACTED] versus placebo on REE	Percentage and absolute change in REE as measured by hood indirect calorimetry in kJ per kg of fat body mass in kJ from Day 16 to 32
Efficacy	To assess the effect of [REDACTED] versus placebo on TEE	Percentage and absolute change in total energy expenditure as measured by doubly labelled water in kJ per kg of fat body mass from baseline (Day 17) to the end of treatment (Day 58 or 59)
Efficacy	To assess the effect of [REDACTED] on measures of body weight and composition versus placebo	
 Absolute change in body weight in kg from Day 17 to 59 Change in absolute and percentage change in total body fat mass as measured by DXA in kg from Day -1 to 59 Change in absolute and percentage change in total body fat mass: lean mass ratio as measured by DXA from Day -1 to 59
Efficacy	To assess the effect of [REDACTED] on glucose homeostasis versus placebo	
 Change in fasting glucose during a MMTT from Day -1 to 59 Percentage change in glucose AUC during a MMTT from Day -1 to 59
Safety	To evaluate the safety and tolerability of [REDACTED] versus placebo	During treatment and follow-up: 
 Vital signs ECGs Safety laboratory analysis TEAEs and TESAEs
Immunogenicity	To characterise the [REDACTED] versus placebo	Development of ADA and titre (if confirmed ADA-positive) during treatment and follow-up

ADA = anti-drug antibodies; AEE = activity energy expenditure; AUC = area under the plasma concentration time curve; DXA = dual-energy X-ray absorptiometry; ECG = electrocardiogram; kg = kilogram; kJ = kilojoule; MMTT= mixed-meal tolerance test; REE = resting energy expenditure; TEAE = treatment-emergent adverse event; TESA = treatment-emergent serious adverse event; TEE = total energy expenditure.

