9 CHANGES TO THE PROTOCOL

9.1 Protocol Amendment 5, 20Mar2019

The changes to text summarised below have been incorporated in the body of Protocol Amendment 5.

Table 9 Summary of Revisions to the Protocol

[figure not shown]

Section of the Protocol Affected	Reason for Amendment
Protocol Synopsis (Objectives and Endpoints; Statistical Methods), Section 2.2 (Secondary Objectives and Endpoints, Table 2, Secondary Objectives and Endpoints), Section 2.3 (Exploratory Objectives and Endpoints, Table 3, Exploratory Objectives and Endpoints), Section 3.2.3.2 (Secondary Endpoints), Section 4.8.1 (General Considerations), Section 4.8.2 (Analysis Populations), Section 4.8.4 (Efficacy), and Section 4.8.8 (Patient Reported Outcomes)	
To correct errors identified in the planned statistical analyses:
 
 The objectives and endpoints were updated. The secondary objective and related endpoint pertaining to the effect of placebo treatment on ad libitum lunchtime energy intake was removed. The rationale for the single-group crossover analyses was removed. Text describing which subjects were to be included in the treatment groups for certain endpoints was removed. Analysis populations were added and revised. The analysis populations were changed for the efficacy and PRO analyses.
Protocol Synopsis (Treatment Groups and Regimens) and Section 3.1.2 (Treatment Regimen)	
The text was revised:
 
 To correct a typographic error in the treatment groups and regimens section of the protocol synopsis. To better clarify the regimen for the single-blind placebo treatment group.
	
Protocol Synopsis (Statistical Methods) and Section 4.8.5.1 (Analysis of Adverse Events)	The terminology for AEs was reconciled to improve consistency and correct typographic errors.
Section 3.1.3 (Dose Escalation)	The text was revised to better clarify how dose escalation will occur from Day 17 onwards.
	

Table 9 Summary of Revisions to the Protocol

Section of the Protocol Affected	Reason for Amendment
Section 4.2.2 (Randomised Treatment Period, Table 6 Treatment Period Study Procedures), Section 4.3.2.7 (Muscle Biopsy), and Section 4.3.2.9 (Intravenous Glucose Tolerance Test)	Minor procedural changes were made: 
 To align with the capabilities of the study site in completing procedures. To correct typographic errors.

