2.1.2 Secondary Study Objectives

- To assess the effect of MEDI0382 titrated up to a dose level of [REDACTED] versus placebo on energy intake during ad libitum lunchtime meals
- To assess the effect of a 16-day period of single-blind placebo on energy intake during an ad libitum lunchtime meal
- To assess the effect of MEDI0382 titrated up to a dose level of [REDACTED] versus placebo on TEE, AEE, and REE as measured by whole room indirect calorimetry
- To assess the effect of a 16-day period of MEDI0382 titrated up to a dose level of [REDACTED] versus placebo on REE
- To assess the effect of MEDI0382 titrated up to a dose level of [REDACTED] versus placebo on TEE as measured by doubly-labelled water
- To assess the effect of MEDI0382 titrated up to a dose level of [REDACTED] on measures of body weight and composition versus placebo
- To assess the effect of MEDI0382 titrated up to a dose level of [REDACTED] on glucose homeostasis versus placebo
- To evaluate the safety and tolerability of MEDI0382 titrated up to a dose level of [REDACTED] versus placebo
- To characterize the immunogenicity profile of MEDI0382 exposure titrated up to a dose level of [REDACTED] versus placebo

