3.4.2.3 Secondary Efficacy Analyses

The analysis of the secondary efficacy endpoints will be performed using the mITT population for endpoints comparing MEDI0382 and placebo during the double-blind treatment period. For secondary efficacy endpoints that allow comparison of MEDI0382 and placebo, the endpoints will be analyzed by an ANCOVA model similar to that used for the primary efficacy analysis. Selected secondary endpoints will also be analysed using the Per-protocol population.

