6 VERSION HISTORY

Version	Date	Summary of Changes	Reason for Change
1.0	10DEC2018	Initial document	Initial document
2.0	23FEB2019	Updates on certain endpoints and analysis populations	Updates needed following protocol amendment

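### SAP v2.0 keeps a secondary objective and endpoint on lunch intake during the placebo run-in that the current protocol does not contain

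*SAP*

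**What the plan says.** - **SAP 2.1.2**, second bullet, sets a secondary objective: "To assess the effect of a 16-day period of single-blind placebo on energy intake during an ad libitum lunchtime meal".
- **SAP 3.4.2.1**, second bullet, gives the matching endpoint: "Percentage and absolute change in total energy intake in kJ during the ad libitum lunch from Day -1 to 16".
- **Protocol synopsis and 2.2, Table 2** have one lunch-intake objective, the effect of MEDI0382 "versus placebo on energy intake during ad libitum lunchtime meals". Its endpoint is "Percentage and absolute change in total energy intake in kJ from the ad libitum lunch from" Day 16 to 32 and Day 16 to 59. There is no Day -1 to 16 interval and no objective on placebo alone.
- **SAP 3.4.2.3** on the model: "For secondary efficacy endpoints that allow comparison of MEDI0382 and placebo, the endpoints will be analyzed by an ANCOVA model". It names the mITT population only for endpoints that compare the two arms in the double-blind period.
- **SAP 3.1** gives a default descriptive summary by treatment for continuous variables. It sets two-sided alpha 0.10 for tests and makes no multiplicity adjustment. **SAP 3.4.2.2** generally requires a baseline and a final measurement, with LOCF where it can be applied.
- **Versions.** The protocol history ends with "Amendment 5, 20Mar2019". SAP Section 6 ends with v2.0, 23FEB2019, for the reason "Updates needed following protocol amendment".

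**The concern.** The two current documents disagree on what the secondary objectives are. Followed as written, the SAP leads to a result reported against an objective that the protocol does not have, under a label (effect of placebo) that the design cannot support. The model and the population for that result would be left to choice after the data are seen.

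**Working it through.** No figure in the plan relates to this endpoint. The sample-size statement concerns body weight and does not enter. The check compares the texts, then makes a count.

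**1. Do the current texts differ?**

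| Lunch-intake interval | Protocol Table 2 | SAP 3.4.2.1 |
|---|---|---|
| Day -1 to 16 | absent | percentage and absolute |
| Day 16 to 32 | percentage and absolute | percentage and absolute |
| Day 16 to 59 | percentage and absolute | percentage and absolute |

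They differ in the first row. This rests on current text only. The amendment log (Protocol 9.1) corroborates that the absence is deliberate: "The secondary objective and related endpoint pertaining to the effect of placebo treatment on ad libitum lunchtime energy intake was removed". It lists this under correction of errors in the planned analyses.

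**2. Dates.** From 23 February to 20 March 2019 is 5 + 20 = 25 days, so the SAP predates Amendment 5 and no later SAP version is listed. Amendments 1 to 4 (the last on 31Aug2018) all predate SAP v1.0 (10DEC2018). The amendment that prompted v2.0 was therefore presumably a draft of Amendment 5; that is an inference.

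**3. Can the change be read as an effect of placebo?** All subjects inject placebo during the 16-day run-in, so there is no concurrent comparison. The two lunches also differ in what precedes them (Protocol 4.2.2, Table 6; 4.3.1; 4.3.2.2):

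| | Day -1 lunch | Day 16 lunch |
|---|---|---|
| Breakfast | Meal Type A, with MMTT sampling | Meal Type A |
| Preceding day | not in the calorimeter | calorimeter stay of up to 36 hours, meals matched to energy expenditure, four 15-minute exercise sessions |
| Dietary advice | none specified | advice for the 72 hours before Day 15 |
| Washout of a second glucose-lowering drug, if stopped 28 days before Visit 4 starts on Day 15 | 28 - 15 = 13 days in | 28 + 1 = 29 days in |

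The day count has no Day 0: the doubly labelled water footnote to Table 6 treats Day 17 as 17 days after Day -1. Any change from Day -1 to 16 mixes these influences with whatever placebo does.

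**4. What analysis rule reaches it?** The ANCOVA and the mITT population in SAP 3.4.2.3 are confined to comparisons of the two arms, so neither covers this endpoint.

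- SAP 3.1 still gives a descriptive summary, but by treatment, which would split a single-group question by later allocation.
- SAP 3.4.2.2 still applies. The footnotes to Table 6 place ad libitum lunches on Days -1, 16, 32 and 59. Nothing lies between Day -1 and Day 16 to carry forward, and SAP 3.1 does not let baseline be carried forward.
- The population matters. ITT includes anyone dosed in the run-in, whereas mITT needs a double-blind dose. Up to five withdrawn subjects may be replaced (Protocol 4.1.7), so the two denominators can differ.

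**5. Count of secondary efficacy variables.** Shared by both documents: lunch Day 16 to 32 and 16 to 59 (4), room calorimetry TEE, AEE and REE (6), hood REE (2), doubly labelled water TEE (2), absolute weight (1), fat mass (2), fat-to-lean ratio (2), fasting glucose (1), glucose AUC (1).

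4 + 6 + 2 + 2 + 1 + 2 + 2 + 1 + 1 = 21. The SAP adds 2, giving 23.

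**6. Would it matter for error rates?** Assume, for illustration only, that every variable is tested at 0.10 and that the tests are independent. The chance of at least one false positive is 1 - 0.9^k:

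- k = 21: 1 - 0.9^21 = 89.1%
- k = 23: 1 - 0.9^23 = 91.1%

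The difference is about two percentage points on a rate that is already uncontrolled by design.

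**The case against.** The best reply is that this is a version lag of 25 days in an exploratory Phase 2a study, and that the harm is slight. By default the SAP yields a descriptive summary of the run-in change, which is close to what one would want anyway. Protocol 4.8.1 gives the SAP the role of adding detail to the protocol's analyses; nothing says that its endpoint list overrides the protocol's. The contrast between the two lunches should also not be overdrawn. The same breakfast type precedes both, and Protocol 4.3.1 prefers that subjects stay at the facility the night before Day -1.

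Most of this stands, and it limits the severity. It does not remove the conflict: the SAP still attaches a secondary objective to the change and names no population. The calorimeter stay before Day 16 and the absence of a control are real.

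A reader might infer more than the documents support:

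- **Two extra tests at alpha 0.10.** The SAP specifies no test for this endpoint. Its alpha applies to tests that are performed and does not call for one on every endpoint.
- **A low bar for significance.** With 24 subjects and a one-sample two-sided test at 0.10, an observed mean change of t(0.95, 23 df)/sqrt(24) = 1.714/4.899 = 0.35 SD of the change would be significant. That describes a test nobody planned. A true shift of that size would reach significance only about half the time.
- **No method at all.** The descriptive default and the missing-data rule do apply. What is missing is a model, test or population specific to the endpoint.

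**Conclusion.** The SAP is wrong as written on this point, and the severity is minor. Sections 2.1.2 and 3.4.2.1 of SAP v2.0 list a secondary objective and endpoint absent from the current protocol. The change they describe is uncontrolled and confounded by the setting, so it cannot be attributed to placebo. Its size is two surplus secondary variables with no planned test; multiplicity is not the argument. The primary endpoint, its ANCOVA, the alpha and the sample size are untouched. The conclusion assumes that Amendment 5 and SAP v2.0 are the versions in force, as their histories indicate.

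**What to change.** Issue a SAP version aligned with Amendment 5 that deletes the second bullet of 2.1.2 and the second bullet of 3.4.2.1.

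If the run-in data are wanted, show Day -1 and Day 16 lunch intake descriptively in one named population. Attach no objective and no hypothesis test, and label the table as run-in data, not as an effect of placebo.

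The cost is SAP wording and at most one changed table. No data collection, randomisation or sample-size change follows.
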